3.2 Secondary objectives and endpoints

Objectives	Endpoints
1. To further evaluate and compare the ability of 2 doses of sD-NLT-AB05 + IL-12 DNA adjuvant followed by 1 or 2 doses of sD-NLT-AB05 + IL-12 DNA adjuvant alone or in combination with Trimer 4571 adjuvanted with 3M-052-AF + Alum to elicit humoral immune responses	a) Neutralizing Ab magnitude and breadth against autologous and tier 1a HIV-1 isolates as assessed by TZM-bl neutralization assay following the third and fourth vaccinations b) Response rate, magnitude, and epitope specificity of HIV-1 specific IgG binding Ab responses as assessed by multiplex assay 2 weeks following third vaccination
2. To further evaluate and compare the ability of 2 doses of sD-NLT-AB05 + IL-12 DNA adjuvant alone or in combination with Trimer 4571 adjuvanted with 3M-052-AF + Alum to elicit cellular immune responses	a) Response rate and magnitude of CD4+ and CD8+ T-cell responses measured by flow cytometry, to HIV-1-specific Env peptide pools, 2 weeks following third vaccination

Objectives	Endpoints

3. To evaluate the durability of cellular and humoral immune responses elicited by 2 doses of sD-NLT-AB05 + IL-12 DNA adjuvant followed by 2 doses of sD-NLT-AB05 + IL-12 DNA adjuvant alone or in combination with Trimer 4571 adjuvanted with 3M-052-AF + Alum
	
a) Magnitude and response rate of CD4 + and CD8+ T-cell responses measured by flow cytometry, to HIV-1-specific Env peptide pools 6 months post last vaccination
 
b) Response rate and magnitude of HIV-1 specific IgG binding Ab responses as assessed by multiplex assay 6 months post last vaccination
 
c) Neutralizing Ab magnitude and breadth against autologous tier 2 HIV-1 isolates as assessed by TZM-bl neutralization assay 6 months post last vaccination

3.3 Exploratory objectives

1. To clinically evaluate EP-injection-related skin changes for 6 months after the last study product administration and subjective assessment by participant of tolerability at 12 months after the last study product administration.
2. To evaluate the response rate and magnitude of HIV-1 specific IgG binding Ab responses as assessed by multiplex assay 2 weeks following second vaccination.
3. To evaluate the response rate and magnitude of CD4 + and CD8+ T-cell responses measured by flow cytometry, to HIV-1-specific Env peptide pools, 2 weeks following the second vaccination.
4. To evaluate the frequency of Env-specific B cells measured by flow cytometry 2 weeks following the second, third, and fourth vaccinations and 6 months post last vaccination.
5. To evaluate serum Ab specificities and elicitation of trimer-degrading Abs using polyclonal epitope mapping as assessed by Electron Microscopy 2 weeks post third and fourth vaccinations.
6. To evaluate the neutralizing Ab magnitude and breadth against heterologous and tier 2 HIV-1 isolates as assessed by TZM-bl neutralization assay following the third, and fourth vaccinations.
7. To evaluate of HIV-1 specific IgG binding Ab responses to the trimer base 2 weeks following second, third, and fourth vaccinations.

8. To evaluate Ab avidity and Fc Receptor functions such as FcR binding, ADCC, antibody-dependent cellular phagocytosis (ADCP), and infected cell antibody-binding assay (ICABA) after the second, third, and fourth vaccinations.
9. To evaluate B-cell receptor (BCR) repertoires and sequences (including analysis of rare B-cell lineages associated with bnAb precursors), including cellular phenotyping and mutational frequency analysis suggestive of somatic hypermutation and affinity maturation following immunization.
10. To characterize monoclonal Abs derived from BCR sequences from Env-specific B cells.
11. To conduct analyses related to furthering the understanding of HIV, immunology, vaccines, and clinical trial conduct.
12. To further evaluate immunogenicity of each vaccine regimen, additional immunogenicity assays may be performed in a subset of participants, including on samples from other timepoints, based on the HVTN Laboratory Assay Portfolio.

4 Laboratory strategy

4.1 Assessment of immunogenicity endpoints

The primary goal of HVTN 304 is to determine whether the sD-NLT-AB05/ IL-12 DNA alone or in a prime-boost regimen with VRC Env Trimer 4571 adjuvanted with 3M-052-AF + Alum will elicit HIV-1 envelope protein specific binding antibody (Ab) and T-cell responses. To this end, HVTN immunogenicity assays will be used to measure both Env-binding Abs and both CD4+ and CD8+ Env-specific T cells.

For the primary endpoints, vaccine matched HIV-specific binding Ab responses will be assessed by multiplex assay, and response rate and magnitude of CD4+ and CD8+ T-cell responses will be assessed by flow cytometry. These data will also be used to identify and prioritize samples for in-depth immunogenicity analyses (secondary and exploratory endpoints, see Sections 3.2 and 3.3).

Additional assays may be performed on selected responders and at additional timepoints at the discretion of Protocol Team leadership based on its evaluation of primary results following the fourth vaccination (see Section 3.1).

The laboratory strategy and the technical details are described in the Central Assay Plan and will be updated as new reagents and techniques are incorporated into assay planning. This document will be available on the protocol webpage. Descriptions of the standard HVTN laboratory assays can be found online at <https://www.hvtn.org/content/dam/hvtn/scientific-programs/hvtn-laboratory-assay-descriptions.pdf>.

5 Study design

This is a randomized trial to examine the safety and immunogenicity of INO-6160 (sD-NLT-AB05/ IL-12 DNA) alone or in combination with Trimer 4571 adjuvanted with 3M-052-AF + Alum in healthy adults. The primary hypothesis is that INO-6160 alone or in combination with Trimer 4571 adjuvanted with 3M-052-AF + Alum vaccinations can induce seroconversion binding antibody responses and induce antigen specific T-cell responses (both CD4+ and CD8+).

5.1 Study population

All inclusion and exclusion criteria must be met for eligibility. Screening procedures to determine eligibility must be performed within 56 days prior to enrollment.

Investigators should always use good clinical judgment in considering a volunteer's overall fitness for trial participation. Some volunteers may not be appropriate for enrollment even if they meet all inclusion/exclusion criteria. Medical, psychiatric, occupational, or other conditions may make evaluation of safety and/or immunogenicity difficult, and some volunteers may be poor candidates for retention.

5.1.1 Inclusion criteria

1. Able and willing to complete the informed consent process, including an Assessment of Understanding: volunteer demonstrates understanding of this study; completes a questionnaire prior to first vaccination with verbal demonstration of understanding of questionnaire items that were answered incorrectly.
2. 18-55 years old, inclusive, on day of enrollment.
3. Available for clinic follow-up through the last clinic visit and willing to be contacted 12 months after the last vaccine administration.
4. Agrees not to enroll in another study of an investigational agent during participation in the trial.
5. In good general health according to the clinical judgment of the site investigator.
6. Physical examination and laboratory results without clinically significant findings that would interfere with assessment of safety or reactogenicity in the clinical judgement of the site investigator.
7. Assessed as low risk for HIV acquisition per low risk guidelines (see [Appendix D](#)), agrees to discuss HIV infection risks, agrees to risk reduction counseling, and

agrees to avoid behavior associated with high risk of HIV exposure through the final study visit. Low risk may include persons stably taking PrEP as prescribed for 6 months or longer.

8. Hemoglobin:

- ≥ 11.0 g/dL for volunteers who were assigned female sex at birth
- ≥ 13.0 g/dL for volunteers who were assigned male sex at birth and transgender men who have been on hormone therapy for more than 6 consecutive months
- ≥ 12.0 g/dL for transgender women who have been on hormone therapy for more than 6 consecutive months
- For transgender participants who have been on hormone therapy for less than 6 consecutive months, determine hemoglobin eligibility based on their sex assigned at birth

9. White blood cell (WBC) count = 2,500-12,000/mm³ (not exclusionary: if count greater than 12,000 with investigation showing general good health and PSRT approval).

10. Platelets = 125,000-550,000/mm³

11. Alanine aminotransferase (ALT) $< 2.5 \times$ upper limit of normal (ULN) based on the institutional normal range

12. Serum creatinine $\leq 1.1 \times$ ULN based on the institutional normal range

13. Blood pressure in the range of 90 to < 140 mmHg systolic and 50 to < 90 mmHg diastolic.

14. Negative results for HIV infection by a Food and Drug Administration (FDA)-approved enzyme immunoassay (EIA) or chemiluminescent microparticle immunoassay (CMIA).

15. Negative for anti-Hepatitis C antibodies (anti-HCV) or negative HCV nucleic acid test (NAT) if anti-HCV antibodies are detected.

16. Negative for Hepatitis B surface antigen.

17. For a volunteer capable of becoming pregnant:

- Volunteers who were assigned female sex at birth and are of reproductive potential must agree to use effective means of birth control from at least 21

days prior to enrollment through 8 weeks after their last scheduled fifth vaccination timepoint (see [Appendix E](#)).

- Has negative β -HCG (human chorionic gonadotropin) pregnancy test (urine or serum) on day of enrollment.
- Volunteers who were assigned female sex at birth must also agree not to seek pregnancy through alternative methods, such as oocyte retrieval, artificial insemination or in vitro fertilization through 8 weeks after their last scheduled vaccination timepoint.

5.1.2 Exclusion criteria

1. Volunteer who is breast-feeding or pregnant.
2. Body mass index (BMI). Enrollment of individuals with $BMI \geq 40$, whom the site investigator assesses are in good health, may be considered by PSRT on a case-by-case basis.
3. Diabetes mellitus (DM). Type 2 DM controlled with diet alone, or a history of isolated gestational diabetes are not exclusionary. Enrollment of individuals with Type 2 DM that is well-controlled on diet alone or on hypoglycemic agent(s) may be considered, provided the HgbA1c is $\leq 8\%$ within the last 6 months (sites may draw these at screening).
4. Previous or current recipient of an investigational HIV vaccine (previous placebo recipients are not excluded).
5. Congenital or acquired immunodeficiency, including systemic medication use likely to impair immune response to vaccine in the opinion of the site investigator such as glucocorticoid use equal to or greater than prednisone 10 mg/day within 3 months prior to enrollment.
6. Blood products or immunoglobulin within 16 weeks prior to enrollment; receipt of immunoglobulin within 16 weeks prior to enrollment requires PSRT approval.
7. Receipt of any live attenuated vaccine within 4 weeks prior to enrollment.
8. ACAM2000 vaccine for Monkeypox received within 30 days prior to enrollment or receipt of study product, or if ACAM2000 received greater than 30 days prior to enrollment, or prior to receipt of study product, vaccination scab still present; or planned administration within 30 days after enrollment or receipt of study product.
9. Receipt of any vaccines that are not live attenuated within 14 days prior to enrollment; replication incompetent vaccines such as the Jynneos vaccine for the prevention of monkeypox disease are not considered to be live vaccines.

10. Receipt of non-HIV experimental vaccine(s) received within the last 1 year. Exceptions may be made by the PSRT for vaccines that have subsequently undergone licensure or Emergency Use Authorization by the FDA or, if outside the United States, by the national regulatory authority or World Health Organization. For volunteers who have received control/placebo in an experimental vaccine trial, the PSRT will determine eligibility on a case-by-case basis.
11. Initiation of antigen-based immunotherapy for allergies within the previous year (stable immunotherapy is not exclusionary); inclusion of participants who initiated immunotherapy within the previous year requires PSRT approval.
12. Receipt of investigational research agents with a half-life of 7 or fewer days within 4 weeks prior to enrollment. If a potential participant has received investigational agents with a half-life greater than 7 days (or unknown half-life) within the past year, PSRT approval is required for enrollment.
13. History of serious reaction (eg, hypersensitivity, anaphylaxis) to any related vaccine or component of the study vaccine regimen.
14. Hereditary angioedema, acquired angioedema, or idiopathic forms of angioedema.
15. Idiopathic urticaria within the past year.
16. Bleeding disorder diagnosed by a doctor (eg, factor deficiency, coagulopathy, or platelet disorder requiring special precautions).
17. Seizure disorder; febrile seizures as a child or seizures secondary to alcohol withdrawal more than 5 years ago are not exclusionary.
18. Asplenia or functional asplenia.
19. Active duty and reserve US military personnel.
20. Any other chronic or clinically significant condition that in the clinical judgement of the investigator would jeopardize the safety or rights of the study participant, including, but not limited to: clinically significant forms of drug or alcohol abuse, serious psychiatric disorders, persons with any suicide attempt within the past one year (if between 1-2 years, consult PSRT) or cancer that, in the clinical judgment of the site investigator, has a potential for recurrence (excluding basal cell carcinoma).
21. Asthma is excluded if the participant has ANY of the following:
 - Required either oral or parenteral corticosteroids for an exacerbation two or more times within the past year; OR

- Needed emergency care, urgent care, hospitalization, or intubation for an acute asthma exacerbation within the past year (eg, would NOT exclude individuals with asthma who meet all other criteria but sought urgent/emergent care solely for asthma medication refills or co-existing conditions unrelated to asthma); OR
 - Uses a short-acting rescue inhaler more than 2 days/week for acute asthma symptoms (ie, not for preventive treatment prior to athletic activity); OR
 - Uses medium-to-high-dose inhaled corticosteroids (greater than 250 mcg fluticasone or therapeutic equivalent per day), whether in single-therapy or dual-therapy inhalers (ie, with a long-acting beta agonist [LABA]); OR
 - Uses more than one medication for maintenance therapy daily. Inclusion of anyone on a stable dose of more than one medication for maintenance therapy daily for greater than two years requires PSRT approval.
22. A participant with a history of an immune-mediated disease, either active or remote. Specific examples are listed in [Appendix F](#) (AESI index). Not exclusionary: 1) remote history of Bell's palsy (>2 years ago) not associated with other neurologic symptoms, 2) mild psoriasis that does not require ongoing systemic treatment
23. Investigator concern for difficulty with venous access based upon clinical history and physical examination. For example, history of IV drug abuse or substantial difficulty with previous blood draws.
24. Presence of implanted electronic medical device (eg, pacemaker, implantable cardioverter defibrillator)
25. Presence of surgical or traumatic metal implant in either upper arm and/or upper torso
26. History of cardiac arrhythmia (eg, supraventricular tachycardia, atrial fibrillation)
(Not excluded: sinus arrhythmia)
27. Tattoo overlying the injection sites preventing assessment of reactogenicity in the view of the investigator or skin condition at the injection sites
28. History or presence of keloid scar formation or hypertrophic scar

5.2 Participant departure from vaccination schedule or withdrawal

5.2.1 Delaying vaccinations for a participant

Under certain circumstances, a participant's scheduled vaccination will be delayed. The factors to be considered in such a decision include but are not limited to the following:

- Intercurrent illness or pre-vaccination abnormal vital signs or clinical symptoms that may mask assessment of vaccine reaction
- Treatment with systemic glucocorticoids (eg, prednisone or other glucocorticoid), immune targeting monoclonal antibodies or other immunomodulators (other than nonsteroidal anti-inflammatory drugs [NSAIDs]), with the exception that study injection may continue per principal investigator (PI) discretion if the next study injection occurs at least 2 weeks following completion of glucocorticoid treatment;
- Receipt of any live attenuated vaccines within 4 weeks prior to study vaccine administration; (Note: ACAM2000 vaccine for Monkeypox received within 30 days prior to enrollment or receipt of study vaccine; or if ACAM2000 received greater than 30 days prior to enrollment or receipt of study vaccine and vaccination scab still present; or planned administration within 30 days after enrollment or receipt of study vaccine).
- Receipt of any vaccines that are not live attenuated vaccines within 2 weeks prior to study vaccine administration. Replication incompetent vaccines such as the Jynneos vaccine for the prevention of monkeypox disease are not considered to be live vaccines.

Vaccinations should not be administered outside the visit window period specified in [Appendix B](#) without PSRT approval.

5.2.2 Discontinuation of study vaccine administration

Under certain circumstances, an individual participant's vaccinations will be permanently discontinued. Specific events that will result in stopping a participant's vaccination schedule include:

- SAE that is subsequently considered to be related to vaccination
- Pregnancy (regardless of outcome)
- HIV infection
- Grade 3 AE assessed as related to study vaccine with the exception of fever and subjective local and systemic symptoms. For grade 3 injection site

erythema and/or induration, upon review, the PSRT may allow continuation of vaccination.

- Grade 4 AE assessed as related to study vaccine
- Clinically significant type 1 hypersensitivity associated with study vaccine

For ease of reference and review, the clinically significant type 1 hypersensitivity definition, as per the Second National Institute of Allergy and Infectious Disease/Food Allergy and Anaphylaxis Network symposium criteria for anaphylaxis (35), is provided below:

1. Acute onset of an illness (minutes to several hours) with involvement of the skin, mucosal tissue, or both (eg, generalized hives, pruritus or flushing, swollen lips-tongue-uvula)

AND AT LEAST ONE OF THE FOLLOWING:

a. Respiratory compromise (eg, dyspnea, wheeze-bronchospasm, stridor, reduced PEF, hypoxemia)

b. Reduced BP or associated symptoms of end-organ dysfunction (eg, hypotonia [collapse], syncope, incontinence)

2. Two or more of the following that occur rapidly after exposure to a likely allergen for that patient [participant] (minutes to several hours):

a. Involvement of the skin-mucosal tissue (eg, generalized hives, itch-flush, swollen lips-tongue-uvula)

b. Respiratory compromise (eg, dyspnea, wheeze-bronchospasm, stridor, reduced PEF, hypoxemia)

c. Reduced BP or associated symptoms (eg, hypotonia [collapse], syncope, incontinence)

d. Persistent gastrointestinal symptoms (eg, crampy abdominal pain, vomiting)

3. Reduced BP after exposure to known allergen for that patient [participant] (minutes to several hours). Adults: systolic BP of less than 90 mm Hg or greater than 30% decrease from that person's baseline

- PI assessment that it is not in the best interest of the participant to continue receiving study vaccine.

- Newly disclosed AESI (see [Appendix F](#))
- Coenrollment in a study with an investigational research agent (rare exceptions allowing for the continuation of vaccinations may be granted with the unanimous consent of the HVTN 304 PSRT)

Participants discontinuing study vaccine for reasons other than HIV infection should be encouraged to participate in follow-up visits and procedures per the protocol for at least 12 months following their last study vaccine administration. At the discretion of the CRS clinician and the PSRT (for composition of PSRT see [Section 9.3](#)), some clinic procedures and sample collections may be modified or discontinued.

If a participant becomes HIV-infected during the course of the study, no additional study vaccine will be administered. Participants will be encouraged to continue scheduled study visits for at least 12 months following their last study vaccine administration. At post-infection follow-up visits, only samples for protocol-specified clinical labs (with the exception of HIV diagnostic testing) will be collected. In addition, some clinic procedures may be modified or discontinued.

5.2.3 Participant departure from vaccine schedule

If a participant misses a scheduled vaccination, they are still eligible to receive future vaccinations.

5.2.4 Discontinuation of study participation

A participant may be discontinued from protocol participation for the following reasons:

- Participant voluntarily withdraws;
- CRS determines the participant is lost to follow-up;
- The investigational new drug (IND) Sponsor or regulatory authorities stop the study; or,
- PI assessment that it is not in the best interest of the participant to continue participation in the study, or that the participant's compliance with the study is not sufficient.

If a participant terminates participation in the study early for any reason, the site PI should consider if the following assessments are appropriate: end-of-study HIV test, CBC with differential, serum chemistry, physical examination, and if indicated, a pregnancy test (see [Appendix A](#)). For participants with HIV infection,

please see Section 8.6. If the site PI has questions regarding a termination visit, they should consult with the PSRT.

6 Statistical considerations

6.1 Sample size justification and accrual

Recruitment will target enrolling 10 healthy, adult participants without HIV per group for the 2 study groups receiving either 2 doses of INO-6160 followed by 2 doses of INO-6160 alone or in combination with Trimer adjuvanted with 3M-052-AF + Alum (for study schema see [Table 1-1](#)). Up to 5 additional participants, or a total of 25 participants, may be enrolled to ensure sufficient samples for immunogenicity analyses, with a goal of at least 20 contributing to the final analyses. Examples of reasons that might necessitate enrollment of additional participants are provided in Section [1.5](#).

Since enrollment is concurrent with receiving the first vaccination, all participants will provide some safety data. It is possible, however, for immunogenicity data to be missing; previous HVTN and AIDS Vaccine Evaluation Group (AVEG) studies suggest 10% is a reasonable estimate for the rate of missing data. For this reason, the sample size calculations account for 10% of enrolled participants having missing data for the primary immunogenicity endpoints. This 10% missingness accounts for both post-processing variables (eg, problems with samples) and is mitigated by the potential for replacing participants who do not continue with the study.

6.1.1 Power calculations for immunogenicity

The main goal for the analysis is to evaluate the difference of the frequency and magnitude of HIV-1 specific binding Ab responses, and the rate of CD4+ and CD8+ T-cell responses between the 2 study groups, following the third and fourth vaccination. The precision with which the true response rate can be estimated from the observed data depends on the true underlying response rate and the sample size. Two-sided 95% confidence intervals (CIs) for the response rate based on observing a particular rate of responses in the study groups is shown in [Table 6-1](#). The table indicates n = 9 per group, assuming a 10% loss of data.

Table 6-1 Two-sided 95% CIs for the true response rate based on observing a particular rate of responses in the study groups, n = 9 (total 10 with 10% missing)

N of responses	Observed response rate (%)	95% CI (%)	
0/9	0	0	37.1
1/9	11.1	0.6	49.3
2/9	22.2	3.9	59.8
3/9	33.3	9	69.1
4/9	44.4	15.3	77.3
5/9	55.6	22.7	84.7
6/9	66.7	30.9	91
7/9	77.8	40.2	96.1
8/9	88.9	50.7	99.4
9/9	100	62.9	100

The estimated differences in response rate, as well as their 95% CIs are shown in [Table 6-2](#). Due to the relatively small sample sizes, it is recommended (36) to construct the two-sided response rate difference CIs with Agresti-Caffo interval (37) that is less conservative. The group with higher response rate is assumed to have positive response rate of 50%, 70%, and 90%, and the assumed range of response rate differences between 2 groups is 0% to 50%, 70%, and 90%, respectively. With sample size of 10 for each group, the statistically significant difference in response rates of approximately 50% (44.4%-55.6%) can be detected while controlling Type-I error rate at 5%.

Table 6-2 Observed rate difference between study groups and their two-sided 95% confidence intervals from 10 total study participants per group. Assuming 10% missing rate for immunogenicity endpoints, n = 9 (total 10 with 10% missing).

Group 1 positive response	Group 2 positive response	Observed rate difference (%)	Rate difference 95% CI (%) (Agresti-Caffo)	
5	5	0	-41.6	41.6
5	4	11.1	-32.5	50.7
5	3	22.2	-22.7	59.1
5	2	33.3	-12.2	66.8

Group 1 positive response	Group 2 positive response	Observed rate difference (%)	Rate difference 95% CI (%) (Agresti-Caffo)	
5	1	44.4	-0.9	73.6
5	0	55.6	11.5	79.4
7	7	0	-37.2	37.2
7	6	11.1	-29.6	47.8
7	5	22.2	-21.3	57.7
7	4	33.3	-12.2	66.8
7	3	44.4	-2.4	75.1
7	2	55.6	8.2	82.7
7	1	66.7	19.7	89.4
7	0	77.8	32.3	95
9	9	0	-24	24
9	8	11.1	-19.3	37.5
9	7	22.2	-13.1	49.5
9	6	33.3	-5.8	60.4
9	5	44.4	2.4	70.3
9	4	55.6	11.5	79.4
9	3	66.7	21.4	87.7
9	2	77.8	32.3	95

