6.4.4 Immunogenicity analyses

6.4.4.1 Statistical Analysis to address primary objectives

The first component of the analysis will entail comparing the frequency of HIV-1–specific binding Ab responses 2 weeks following the fourth vaccination. Comparison between the 2 vaccine groups will use Fisher's exact test, while

McNemar's test will be used for paired data (between visits), with a significant difference declared if the 2-sided p-value is ≤ 0.05 .

To compare the magnitude of HIV-1-specific binding Ab responses 2 weeks following the fourth vaccination. Between the 2 vaccine groups, a two-sided Wilcoxon rank sum test with 5% type-I error rate will be performed. Wilcoxon signed rank test with 5% type-I error rate will be performed for paired data.

With the response rates of CD4+ and CD8+ T cell to HIV-1 specific Env peptide pools 2 weeks following the fourth vaccination, the 2 vaccine groups will be compared using Fisher's exact test, and McNemar's test will be used for paired data), with a significant difference declared if the 2-sided p-value is ≤ 0.05 . For each T-cell subset, the positivity call for each peptide pool will include a multiple-comparison adjustment for the number of peptide pools used in the assay using the discrete Bonferroni adjustment. The magnitude of response will be analyzed with two-sided Wilcoxon rank sum test for independent data and Wilcoxon signed rank test for paired data, with 5% type-I error rate. Graphs will be used to display the background-subtracted magnitudes for each participant by protein, treatment arm, and timepoint, with a box plot of data from positive responders superimposed on the individual data values. Statistical testing comparing the magnitudes will be based on positive responders only.

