#### **4 COHORT DEFINITION**

A total of 20 participants were enrolled in the study, 10 in Group 1 and 10 in Group 2.

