### 7.2 General approach

For the statistical analysis of immunogenicity endpoints, data from enrolled participants will be used according to the initial randomization assignment regardless of how many injections they received. Additional analyses may be performed, limited to participants who received all scheduled injections per protocol. Assay results that are unreliable, from specimens collected outside of the visit window, or from HIV-infected participants are excluded. Since the exact date of HIV infection is unknown, any assay data from blood draws 4 weeks, or less, prior to an infected participant's last seronegative sample and thereafter may be excluded. If an HIV-infected participant does not have a seronegative sample post enrollment, then all data from that participant may be excluded from the analysis.

Discrete categorical assay endpoints (eg, response rates) will be analyzed by tabulating the frequency of positive response for each assay by antigen and treatment arm at each timepoint for which an assessment is performed. Crude response rates will be presented with their corresponding 95% CI estimates calculated using the score test method (1). Barnard's tests will be used to compare the response rates between 2 vaccine groups at a given time-point, McNemar's tests will be used for paired data (between visits), with a significant difference declared if the 2-sided p-value is  $\leq 0.05$ .

For quantitative assay data (eg, magnitude of HIV-1 Env-specific binding Ab responses), graphical and tabular summaries of the distributions by antigen, treatment arm, and timepoint will be made. The difference between arms at a specific timepoint will be tested with a nonparametric Wilcoxon rank sum test and the difference between visits will be tested with a nonparametric Wilcoxon signed rank test including all available data regardless of response positivity. Response magnitudes below the limit of detection of the assay will be replaced by half of the limit in the

tests. All statistical tests will be 2-sided and will be considered statistically significant if  $p \leq 0.05$ .

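### Protocol 6.1.1's detectable difference of about 50 points is the smallest observed difference that reaches significance; power at a true 50-point difference is only about 53-58% with 9 evaluable per group

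*Protocol*

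**What the plan says.** Protocol 6.1.1 sets the aim: "The main goal for the analysis is to evaluate the difference of the frequency and magnitude of HIV-1 specific binding Ab responses", together with the T-cell response rates, between the two groups. It tabulates Agresti-Caffo 95% intervals for the difference in response rate (Table 6-2), captioned as observed differences with n = 9 (10 enrolled less 10% missing). On the scenarios it says: "The group with higher response rate is assumed to have positive response rate of 50%, 70%, and 90" per cent. It concludes, beginning "With sample size of 10 for each group", that "the statistically significant difference in response rates of approximately 50% (44.4%-55.6%) can be detected while controlling Type-I error rate at 5" per cent. No power or target power appears in the section.

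Section 6.1 of the protocol enrols 10 per group, allows up to 5 more, "with a goal of at least 20 contributing to the final analyses". SAP section 4 reports: "A total of 20 participants were enrolled in the study, 10 in Group 1 and 10 in Group 2".

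The two documents name different tests for the comparison. Protocol 6.4.4.1: "Comparison between the 2 vaccine groups will use Fisher's exact test". SAP 7.2: "Barnard's tests will be used to compare the response rates between 2 vaccine groups". Both are two-sided with p ≤ 0.05.

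**The concern.** A difference that can be detected, stated under a heading about power and alongside assumed response rates, will be read as a true difference the trial has a good chance of finding. The quoted figures look instead like a threshold on the observed difference. When the true difference equals such a threshold, the observed difference falls short of it roughly half the time.

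This is the plan's only statement of what the between-group comparison of response rates can find, and the section calls that comparison its main goal. If the sentence is taken at face value, a non-significant result could be reported as evidence against a 50-point gain from adding the protein, when the trial would often miss a gain of that size.

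**Working it through.** **Inputs.** Two-sided 5% level (protocol 6.4.4); 9 evaluable per group (6.1 and 6.1.1), with 10 as the alternative if nothing is missing; Agresti-Caffo interval (6.1.1); Fisher's test (protocol 6.4.4.1); Barnard's test (SAP 7.2).

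**Step 1: reproduce the plan's figures.** With x₁ and x₂ responders out of n per group, let p̃ᵢ = (xᵢ + 1)/(n + 2). The interval is

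(p̃₁ − p̃₂) ± 1.96 × √{[p̃₁(1 − p̃₁) + p̃₂(1 − p̃₂)]/(n + 2)}.

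- 9/9 v 5/9: 10/11 − 6/11 = 0.364, SE 0.173, interval 2.4 to 70.3.
- 7/9 v 2/9: 8/11 − 3/11 = 0.455, SE 0.190, interval 8.2 to 82.7.
- 7/9 v 3/9: 8/11 − 4/11 = 0.364, SE 0.198, interval −2.4 to 75.1.

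These match Table 6-2, as do its other rows.

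**Step 2: what 44.4-55.6 is.** Over all 100 outcome pairs at n = 9, the smallest observed differences whose interval excludes zero are 4 v 0 and 9 v 5 (4/9 = 44.4 points) and 5 v 0, 6 v 1, 7 v 2 and 8 v 3 (5/9 = 55.6 points). That is exactly the quoted range, so it is a significance boundary on the observed difference.

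The same enumeration at n = 10 gives 40 points (4 v 0, 10 v 6) and 50 points (5 v 0, 6 v 1, 7 v 2, 8 v 3, 9 v 4). The sentence speaks of 10 per group but quotes ninths.

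**Step 3: which test has this boundary.** Barnard's test rejects for exactly the same outcomes as the Agresti-Caffo rule at n = 9 and n = 10. Its maximum Type I error is 3.3% and 4.2%, so the Type I statement is correct. Fisher's test does not share the boundary at n = 9:

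| Outcome | Fisher p | Barnard p |
|---|---|---|
| 9 v 5 | 0.082 | 0.033 |
| 7 v 2 | 0.057 | 0.031 |
| 8 v 3 | 0.0498 | 0.021 |
| 5 v 0 | 0.029 | 0.010 |

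Fisher's boundary at n = 9 is 55.6-66.7 points.

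**Step 4: power at a true 50-point difference.** Power is the sum, over rejected pairs, of Bin(x₁; n, p₁) × Bin(x₂; n, p₂). For 75% v 25% at n = 9 with Barnard's test:

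| x₁ | P(x₁) | Rejects if x₂ ≤ | P(x₂ that low) | Product |
|---|---|---|---|---|
| 4 | 0.0389 | 0 | 0.0751 | 0.0029 |
| 5 | 0.1168 | 0 | 0.0751 | 0.0088 |
| 6 | 0.2336 | 1 | 0.3003 | 0.0702 |
| 7 | 0.3003 | 2 | 0.6007 | 0.1804 |
| 8 | 0.2253 | 3 | 0.8343 | 0.1879 |
| 9 | 0.0751 | 5 | 0.9900 | 0.0743 |

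The total is 0.525; rejections in the wrong direction add nothing visible. Repeating this for other pairs gives power in per cent:

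| True rates | Barnard n=9 | Barnard n=10 | Fisher n=9 | Fisher n=10 |
|---|---|---|---|---|
| 75 v 25 | 52.5 | 61.9 | 42.8 | 42.1 |
| 70 v 20, 80 v 30 | 52.9 | 62.2 | 43.8 | 42.6 |
| 60 v 10, 90 v 40 | 57.9 | 65.9 | 48.6 | 47.4 |
| 55 v 5, 95 v 45 | 64.3 | 71.8 | 50.2 | 53.4 |
| 50 v 0, 100 v 50 | 74.6 | 82.8 | 50.0 | 62.3 |

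**Step 5: the two quoted ends (Barnard, n = 9).** A true 44.4-point difference has 42-48% power when the higher rate is 55.6-90%, and 62.6% at 44.4 v 0 or 100 v 55.6. A true 55.6-point difference has 63-68% when the higher rate is 70-90%, and 84.3% at 55.6 v 0 or 100 v 44.4.

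**Step 6: difference needed for 80% power (Barnard), in points.**

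| Higher rate (%) | 70 | 75 | 80 | 85 | 90 | 100 |
|---|---|---|---|---|---|---|
| n = 9 | 62.2 | 63.7 | 64.4 | 64.4 | 63.3 | 52.9 |
| n = 10 | 58.8 | 59.5 | 59.7 | 59.4 | 58.4 | 48.4 |

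**Step 7: scenario labels.** The tabulated higher counts are 5/9, 7/9 and 9/9, which are 55.6%, 77.8% and 100%, not the stated 50%, 70% and 90%. Within Table 6-2 the 44.4-point end comes only from the 9/9 rows. At 8/9 (88.9%), the count nearest to 90%, the boundary is 55.6 points.

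**The case against.** The table is correct, its caption says the differences are observed, and the section opens by talking about precision. It promises no power, and the sentence itself speaks of statistical significance. On that reading it describes a boundary, loosely worded. The 10 per group can be read as enrolled, since the 10% loss is stated nearby. The counts 5, 7 and 9 are exactly 50%, 70% and 90% of 10, so the table rather than the text may have departed from the intended scenarios. The choice between Fisher and Barnard is a separate conflict. A 20-person phase 1 trial need not have 80% power, and its primary hypothesis is that the regimens elicit responses.

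Much of this stands. There is no error in the table, 10 can mean enrolled, the documents do not show which side of the percentage mismatch was intended, and the printed intervals limit over-reading. It does not rescue the sentence. Calling a difference detectable, under a power heading and with assumed rates, invites the wrong reading. Protocol 6.1.2 shows the proper form for safety: a true event rate of 20.6% paired with a 90% chance of seeing at least one event. Nor can the test be set aside, because the boundary fails under the one the protocol itself names.

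**Conclusion.** The point holds and should be fixed. The quoted 44.4-55.6 points is the observed-significance boundary at 9 evaluable per group, not a difference the trial is likely to detect. With Barnard's test at n = 9, a true 50-point difference is missed about 42-47% of the time for pairs from 60 v 10 to 90 v 40. With all 10 per group evaluable, it is missed about 34-38% of the time (100 minus 61.9-65.9). Power is higher only as one rate nears 0% or 100%.

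These figures assume independent binomial responses, equal evaluable numbers per group and a two-sided 5% level. The documents set no target power; 80% is used here only as a familiar reference. The conclusion does not depend on it, nor on which scenario labels were intended.

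**What to change.** 1. Describe 44.4-55.6 points as the smallest observed difference reaching significance with 9 evaluable per group, and add 40-50 points for 10 evaluable.
2. Reconcile the scenario percentages with the counts. If Table 6-2 stays as printed, the text should read 55.6%, 77.8% and 100%.
3. State exact power for the test to be used. For Barnard's test, for example: with 9 evaluable per group, power for a true 50-point difference is about 53-58% away from the extremes (up to 75% at 50% v 0% or 100% v 50%), and 80% power needs about 62-64 points with the higher rate at 70-90% (about 53 if it is 100%). With 10 evaluable, the figures are 62-66% (up to 83%) and 58-60 points (about 48).
4. Name the same between-group test in the protocol and the SAP. If Fisher's is kept, the boundary at n = 9 becomes 55.6-66.7 points and power at 50 points is about 43-49% over the same range.

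The cost is wording and a less favourable sensitivity figure. Enrolment and endpoints are unaffected, and the intervals in Table 6-2 need no correction. Since enrolment is complete, the corrected statement can go in the SAP and the final report, so that a non-significant comparison is read alongside its interval.
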